- **Usability and User testing:** We will recruit six Spanish speaking pregnant Hispanic rural women at the RWMC, Scottsbluff to interact with the system. They will be enrolled at the Regional West Medical Center (RWMC), Scottsbluff, NE. [name] and [name] (Consultant) will be responsible for subject recruitment. Information flyers will be available at the RWMC to inform the subjects about the study. These subjects will not be part of the actual study. After a brief introduction to the system, study subjects will be asked to complete a predefined set of tasks by interacting with the system and the duration of this interaction will be around 30 minutes. We will have a think aloud protocol that will involve participants thinking aloud as they perform a set of specified tasks. Users will be asked to say whatever they are looking at, thinking, doing, and feeling, as they go about their task. This will enable observers to see first-hand the process of task completion. Notes and test sessions will be audio taped of everything that users' say, without attempting to interpret their actions and words will be taken. During these assessments, we will gather basic quantitative results including information about the time required to complete tasks and the errors encountered using the usage data metrics as described previously (Section II. Conceptual framework). A likert scale survey will be used to assess user satisfaction with the computer program and any recommendations study subjects may have to improve the system. The results of the user testing will be followed by incorporating the recommended changes to the design of the Computer-based Breast-feeding educational support program during months 6 and 7. The final program will be deployed during month 8 of the study period.

IV. Research Design and Methods

The proposed pilot study is a two-group repeated measures quasi-experimental design that will be used to explore the effect of using Computer based Breast-feeding Educational Support program to promote breast-feeding in rural Hispanic women. (Figure4)

Control	Confounders	Primary Outcome
	Socio-demographics Breast-feeding status	Partial or Exclusive Breast-feeding till six months (Proportion)

[figure not shown]
[figure not shown]

Figure4.Research Design

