Baseline data will be gathered during the enrollment prenatal visit (anytime during last six weeks of pregnancy) and follow up data will be collected on postpartum day 3, week 6 and months 3 and 6 resulting in overall five data collection time periods. The postpartum day 3 data collection will be done over the telephone while other follow up data collection including week6 and months 3 and 6 will be done when the individuals in both the groups will come to the hospital for follow up educational sessions. Almost all women who initiate breast-feeding plan to continue for at least 6 weeks; however, one of every five women quits breast-feeding within the first days after delivery⁷³. This finding supports the notion that 2–4 weeks postpartum is a vulnerable period for breast- feeding cessation⁷⁴. Baseline evaluation will be done during the prenatal visit (last trimester). The research assistant will schedule a follow up interview to administer the study questionnaires at a convenient time over the telephone. Subjects will receive gift vouchers worth \$15 for baseline and for every follow up postpartum visit (Table2).

Pre and Post educational Session data collection	Baseline	Day 3	Week 6	Month 3	Month 6
Socio-demographics	X				
Health Literacy	X				
Breast-feeding Knowledge	X	X	X	X	X
Breast-feeding self-efficacy	X	X	X	X	X
Intent to Breast-feed	X	X	X	X	X
Breast-feeding attitudes	X	X	X	X	X
Perceived norms	X	X	X	X	X
Program acceptance	X				X

Table2. Data Collection in intervention and attention control groups

Informed Consent

[name] (Consultant) is a bilingual and certified Spanish translator and will administer the informed consent and assent forms at the RWMC, Scottsbluff after the eligible subjects have agreed to participate in the study. The research staff members will read the UNMC IRB-approved consent and assent forms to subjects describing the study, the measures used by the researchers to protect the confidentiality of the responses, and the voluntary nature of the study. Those who agree to participate will be asked to sign the consent and the assent forms as appropriate. The research staff member will countersign the consent and the assent forms and copies will be given to the participant.

Data Entry and Quality Assurance

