In the first step of exploratory analysis, we will present a table to summarize the distribution of all variables, including outcomes, confounding, and process variables. This table will also serve the purpose of quality control of the original data, to mine missing data patterns and outliers. The distributions of the continuous outcomes will be explored for normality and transformations will be used if warranted. Continuous variables will be summarized using means, medians, standard deviations and ranges while categorical variables will be examined using frequencies and percentages. Exploratory analysis on process variables will be used for post-hoc analysis. Inter-rater reliability of knowledge, attitudes/beliefs, self-efficacy and intent to breast feed will be examined using the kappa statistic.

Sample Size Justification

The optimum number of participants for a focus group is typically 6-10 people with similar backgrounds who participate in the interview for one to two hours may vary⁵². The number generally suggested as being manageable is between six and ten participants as smaller groups show greater potential and large enough to gain a variety of perspectives and small enough not to become disorderly or fragmented⁵². For the intervention effect analysis, a comparison of two independent binomial proportions using Pearson's Chi-square statistic with a two-sided significance level of 0.05, a sample size of 23 per group achieves a power of at least 0.8 when the proportion with partial breast-feeding at 6 months are 0.3 for the control group and 0.7 for the intervention group. To account for anticipated attrition of 15%, the sample size will be increased to 54 subjects (27 per group). This is a pilot study to explore the possibility of promoting breast-feeding using computer based breast-feeding tailored educational program among Hispanic rural women.

Statistical Analysis

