Baseline characteristics will be summarized by intervention group. A chi-square test will be used to compare baseline categorical variables between the intervention and control groups and a t-test will be used for continuous variables. The primary outcome of proportion partial or exclusive breast-feeding at 6 months will be compared between groups using a Chi-square test. The primary outcome will be assessed at 6 months; however, we will also conduct these analyses at 6 weeks and 3 months. A generalized linear mixed model using a binomial distribution and logit link function will be used to examine partial breast-feeding at day 3, week 6 and months 3 and 6 postpartum, with intervention group as a fixed effect and subject as a random effect using a Variance Components covariance structure. In exploratory analyses, covariates will be added to the model to adjust for confounders that differ significantly between both the intervention and attention control groups at the 0.20 level of significance. Similar analyses will be conducted to examine exclusive breast-feeding. Breast-feeding knowledge, self-efficacy, will be compared between groups using a t-test. In exploratory analyses, a general linear mixed model with intervention group as a fixed effect and subject as a random effect using an AR (1) covariance structure will be examined. Covariates will be added to the model to adjust for confounders that differ significantly between both the intervention and attention control groups at the 0.20 level of significance (Table3).

Variables Assessment	Variable types	Data Analysis	Anticipated Outcomes
Focus groups	Qualitative	Framework analysis	Breast-feeding educational modules and functionality of the computer based program established
Socio-Demographics	Continuous & Categorical	T test for continuous and Chi-square tests for categorical variables.	Distribution of population characteristics
Intent to Breast-feed	Categorical	Chi-Square test	Assess intent to breast-feed

Breast-feeding knowledge	Continuous	T test	Improve Breast-feeding knowledge (intervention)
Breast-feeding attitudes and beliefs	Continuous and categorical	T test for continuous and Chi-square tests for categorical variables.	Change Breast-feeding related attitudes and beliefs
Breast-feeding perceived norms	Continuous and categorical	T test for continuous and Chi-square tests for categorical variables.	Change Breast-feeding related behavior

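### Both mixed models name intervention group as their only fixed effect, so the plan has no covariate-adjusted month-6 estimate and the pooled effect they give is not the month-6 effect

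*Combined protocol and SAP*

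**What the plan says.** All of this is in the combined protocol and SAP, section VII (Analysis Plan), under Statistical Analysis, unless another place is named.

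- The primary outcome, partial or exclusive breast-feeding at 6 months, is compared by an unadjusted chi-square test. For the earlier visits, "we will also conduct these analyses at 6 weeks and 3 months".
- A binomial mixed model with logit link covers day 3, week 6 and months 3 and 6, "with intervention group as a fixed effect and subject as a random effect using a Variance Components covariance structure". Exclusive breast-feeding is to be handled in the same way.
- Knowledge and self-efficacy are compared by t-test and, as exploratory analysis, by "a general linear mixed model with intervention group as a fixed effect and subject as a random effect using an AR (1) covariance structure".
- Adjustment is attached to these two models only: "covariates will be added to the model to adjust for confounders that differ significantly" between the groups at the 0.20 level. Every entry in Table 3 for a between-group comparison is an unadjusted t-test or chi-square test.
- Under Data Collection procedures, "follow up data will be collected on postpartum day 3, week 6 and months 3 and 6 resulting in overall five data collection time periods". Which of the five enter the linear model is not stated.

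AR(1) and variance components describe covariance, not the mean. Nothing else in the Analysis Plan, including Table 3, adds a term for time.

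**The concern.** The documents expect the outcome to change across the modelled visits. Data Collection procedures reports that "one of every five women quits breast-feeding within the first days after delivery", and the Background gives US rates of 75% initially and 43% at 6 months. A model with group as its only fixed effect fits one constant level per arm to a falling outcome.

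Two things follow.

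1. The one thing a model could add to the month-6 chi-square is adjustment for chance imbalance, and as specified that adjustment applies only to a visit-pooled quantity.
2. With no visit term, an arm that loses more women after the early visits keeps a larger share of high-rate early observations. Its fitted level then rises even if the loss is completely random.

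**Working it through.** **The plan's own figure.** Sample Size Justification gives 23 per group for 0.3 vs 0.7, two-sided 0.05, power at least 0.8. Exact power of the uncorrected Pearson test is 0.809 at 23 per group and 0.840 at 27, so the figure reproduces. Inflation: 23 × 1.15 = 26.45, rounded up to 27 per group, or 54. None of this uses the mixed models.

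**Inputs.** From the plan: the month-6 rates 0.3 and 0.7, the visits and the model form. Assumed: all other rates. Control is set at 0.80/0.60/0.45/0.30 (day 3, week 6, month 3, month 6), the first value following the one in five who quit early. Three intervention paths all end at 0.70:

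- building: 0.80/0.75/0.72/0.70
- intermediate: 0.88/0.82/0.77/0.70
- constant: 0.956/0.891/0.817/0.70

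**Step 1: pooled coefficient against month-6 effect, no dropout.** The month-6 odds ratio is (0.7/0.3)/(0.3/0.7) = 5.44 for every path (log 1.69). The control average over visits is (0.80 + 0.60 + 0.45 + 0.30)/4 = 0.5375. The path averages are 0.7425, 0.7925 and 0.841, so the visit-averaged differences are 0.205, 0.255 and 0.303, against 0.40 at month 6. The large-sample group odds ratio from the model as written depends on how a woman's visits are related:

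| Within-woman histories | Building | Intermediate | Constant |
|---|---|---|---|
| Random intercept, SD 1 | 2.8 | 3.8 | 5.2 |
| Random intercept, SD 2 | 3.7 | 5.2 | 7.3 |
| Random intercept, SD 3 | 4.9 | 7.2 | 9.8 |
| No woman restarts (log OR 2.73/2.82/2.85) | 15 | 17 | 17 |

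Part of any gap from 5.44 is scale, because a mixed model's odds ratio is subject-specific. On that scale the month-6 odds ratio is 7.67 at SD 1 and 15.93 at SD 2, and the pooled values in those rows still fall short of it.

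**Step 2: unequal loss, no true effect.** Put 0.80/0.60/0.45/0.30 in both arms and lose control women at random after week 6. The control average becomes

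- 15% lost: (0.80 + 0.60 + 0.85 × 0.45 + 0.85 × 0.30)/3.7 = 0.551
- 30% lost: (0.80 + 0.60 + 0.70 × 0.45 + 0.70 × 0.30)/3.4 = 0.566

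against 0.5375 in the complete arm. In the group-only mixed model the false log odds ratio is:

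| Loss, control vs intervention | Random intercept, SD 1 to 3 | No restarts |
|---|---|---|
| 15% vs 0% | -0.07 to -0.12 | -0.147 |
| 30% vs 0% | from -0.14 at SD 1 | -0.307 |
| 20% vs 10% | not run | -0.10 |
| 15% vs 15% | 0 | 0 |

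With 27 per arm and no restarts, the sampling SD is about 0.8. Type I error is 0.048 with no loss, 0.057 at 15% vs 0% and 0.080 at 30% vs 0% (1000 replicates, Monte Carlo SE about 0.007). In a separate run with random-intercept histories and a day-3 rate of 0.75, adding visit brought the false effect to 0.000 in every dropout split tried.

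**Step 3: linear model.** If baseline is one of the five responses, its weight under AR(1) is 1/(2 + 3(1 - ρ)) = 0.244, 0.286 or 0.345 at ρ = 0.3, 0.5 or 0.7. A constant post-baseline effect then shrinks to 0.76, 0.71 or 0.66 of its size. Bias from unequal dropout is small here, about 0.02 to 0.05 SD.

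**Step 4: what adjustment at month 6 would address.** Suppose there is no effect, a binary covariate is split 60% vs 40%, and month-6 rates are 0.46 with it and 0.14 without. The arm rates are 0.6 × 0.46 + 0.4 × 0.14 = 0.332 and 0.4 × 0.46 + 0.6 × 0.14 = 0.268, a log odds ratio of 0.31 from imbalance alone.

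**The case against.** The strongest reply is that this is silence, not exclusion. Section IV says "The proposed pilot study is a two-group repeated measures quasi-experimental design", the model lists its four visits, and AR(1) needs them in order, so visit terms may well have been intended. That is fair, and nothing here shows a decision to leave time out. But an analyst following the text would fit group alone, and the adjusted month-6 contrast depends on the missing terms.

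Four further points stand in whole or in part.

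- **Limited reach.** The adjusted models and the linear model are labelled exploratory, in a pilot. Unadjusted comparisons exist at week 6, month 3 and month 6. Women are randomised, so adjustment deals only with chance imbalance. All of this stands, although the unadjusted logistic mixed model carries no exploratory label.
- **Dropout.** A reader might infer that dropout seriously biases the mixed model. The plan anticipates 15% attrition overall, without a difference between arms. The shift is zero at equal loss and small against its sampling error at 15% vs 0%; 0.057 cannot be told from 0.048. Only 30% vs 0% shows inflation.
- **Timing.** A reader who looks only at the no-restart row might infer that the pooled odds ratio hardly depends on when the effect appears. That holds only under that assumption; with random intercepts it roughly doubles from building to constant.
- **Choice of model.** A GEE might seem required. It is not. The case for it rests on women rarely restarting, which the documents do not establish. If partial feeding is taken literally as mixed feeding, women can move into it from exclusive feeding.

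**Conclusion.** The point holds as an incomplete specification that affects secondary interpretation. As written, both models give a visit-pooled effect, and the plan has no covariate-adjusted estimate at month 6, its primary time point. The pooled odds ratio should not be read beside the month-6 test as the same quantity: depending on timing and within-woman dependence it runs from about 2.8 to 9.8, or 15 to 17 with no restarts, for one and the same month-6 comparison. The dropout shift is real but modest, and it needs unequal loss.

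A reader might infer that the primary analysis or the sample size is compromised. The documents do not support that: the chi-square uses month-6 data only and the 54 subjects rest on it. This says nothing either way about outcome-related dropout at month 6.

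The missing wording is certain. The sizes rest on assumed rates before month 6, assumed dependence and assumed dropout splits, because the documents give none. The change should be made, but the primary result does not depend on it.

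**What to change.** Add categorical visit and group-by-visit as fixed effects to both mixed models. Report the month-6 contrast, unadjusted and covariate-adjusted, as supportive of the chi-square. A visit-averaged effect from the same model may stay as a secondary summary. For knowledge and self-efficacy, state that the post-baseline visits are the responses and that the baseline score, already collected under Table 2, is a covariate.

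For the binary outcomes, allow a GEE with the same terms and small-sample standard errors if few women restart and the mixed model is unstable. With no restarts, the mixed model with visit terms has no finite maximum. With 2%, 5% or 10% restarting per visit, its month-6 log odds ratio is 7.7, 5.4 or 3.9, against 1.69 on the marginal scale.

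Costs: no new data, but more parameters (2 to 8 in the mean model for the binary outcomes). If the effect is constant over visits, power is lower than for the pooled model: about 0.74 for the GEE month-6 contrast against 0.84 at 23 per arm, in simulations without restarts. The GEE visit-averaged effect does not recover this (0.72). The contrast adds no power to the month-6 chi-square (0.74 against 0.81 at 23 per arm, about equal at 27). With two strong covariates entered by the 0.20 rule, the GEE failed in 7 of 400 simulated trials at 23 per arm and 3 of 400 at 27.

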Acceptance of Computer-based Breast-feeding Educational Support program: We will adapt and use previously published questionnaire used to assess acceptance of computer based asthma educational program⁴⁶ (Appendix F). Feedback will be gathered on ease of use of program, navigation patterns, and feedback during the program, future use of program and recommendation to others to use the program. Usage data analysis will help to understand learning patterns during use of the computer program by gathering the amount of time an individual spent on viewing the educational modules.

d. Potential Confounders

Socio-demographics: Include age, income levels, employment status, and education level, smoking status, prior pregnancies and previous history of breast-feeding. Information is also gathered about prior use of computers, its frequency of usage prior use of internet and sources of health information (Appendix G). Health literacy is the ability to perform basic reading and numerical tasks required to function in the health care environment⁶⁵. Studies have shown an association between limited health literacy and worse health outcomes such as poorer knowledge about health conditions^{66, 67}. The 3 health literacy screening questions, which performed optimally in a previous study⁶⁸, will be used to assess health literacy assessments of Hispanic rural women (Appendix H) and include: "How often do you have someone (like a family member, friend, hospital/clinic worker or caregiver) help you read hospital materials?" (Help Read), "How often do you have problems learning about your medical condition because of difficulty understanding written information?" (Problems Reading), and "How confident are you filling out forms by yourself?" (Confident with forms). Responses will be scored on a Likert scale from 0 to 4 and were asked to choose between all of the time, most of the time, some of the time, a little of the time or none of the time⁶⁸.

In addition, Newest Vital Sign (NVS) consisting of a nutrition label with 6 accompanying questions to assess literacy will be used⁶⁹. It takes approximately 3 minutes to administer, and is meant to allow healthcare providers to make a quick assessment of patients' literacy, which can then allow them to adapt communication to achieve better outcomes. It assesses literacy and numeracy, and is available in both English and Spanish versions. The

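### Continuous process scores are compared by an unadjusted t-test with no visit or score form named, and exploratory covariates are chosen by a between-arm 0.20 screen; baseline-adjusted analysis with a fixed covariate list would be better at little cost.

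*Combined protocol and SAP*

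**What the plan says.** Table 2 schedules knowledge, self-efficacy, attitudes and perceived norms at baseline, day 3, week 6, month 3 and month 6, "resulting in overall five data collection time periods". For the scores, the Statistical Analysis section states only that "Breast-feeding knowledge, self-efficacy, will be compared between groups using a t-test". Table 3 lists a t-test for knowledge, self-efficacy and the continuous parts of attitudes and norms. Its anticipated-outcome column uses words of change, for example "Change Breast-feeding related attitudes and beliefs", but does not define the quantity to be tested. Visits are named for the breast-feeding outcome (6 months, with 6 weeks and 3 months also analysed) but not for these scores.

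The longitudinal alternative, placed under exploratory analyses, is "a general linear mixed model with intervention group as a fixed effect and subject as a random effect" with an AR(1) structure. No time, group-by-time or baseline term is mentioned. In this model and in the exploratory breast-feeding models, covariates are added to "adjust for confounders that differ significantly between both the intervention and attention control groups at the 0.20 level of significance". The socio-demographic candidates under Potential Confounders "Include age, income levels, employment status, and education level, smoking status, prior pregnancies and previous history of breast-feeding"; computer use, information sources and health literacy follow. Baseline process scores are not on that list.

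The Exploratory Data Analysis section says "Exploratory analysis on process variables will be used for post-hoc analysis".

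**The concern.** Four follow-up visits and two score forms give eight different t-tests per score, all of which fit the text. Table 4 schedules analysis and initial findings at months 6, 12 and 20, while data collection runs from month 8 to month 20. The choice among the eight could therefore be made after some results are known. Knowledge and self-efficacy are also named in the study objective, and the pilot is meant to lay the ground for a larger trial, so a clearly defined effect estimate is one of the things it should hand on.

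Two statistical losses follow. The baseline score is collected but not used, which gives up precision whenever baseline and follow-up correlate. And a between-arm significance screen is a poor way to choose covariates in a randomised comparison: a variable fixed before allocation passes it about 20% of the time whatever its relation to the outcome. The threshold is set in advance, but the covariate set it yields is not.

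**Working it through.** **Inputs.** From Sample Size Justification: 23 per group, two-sided 0.05, power at least 0.8, 27 per group enrolled with 15% attrition. From Table 2: baseline plus four follow-ups. From Potential Confounders: seven socio-demographic items. The documents give no correlation *r* and no R-squared, so all values of these below are assumptions.

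**The plan's own figure.** The 23 per group is for the binary primary outcome (0.3 against 0.7). Exact enumeration of Pearson's chi-square gives power 0.809 at 23 per group, so it reproduces. Attrition leaves 27 × 0.85 = 22.95 per group. The plan states no figure for the continuous scores; 23 per arm is used below.

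**1. Precision.** In SD units, the variance of the group difference is (2/23) × *f*:
- follow-up t-test: *f* = 1
- change-score t-test: *f* = 2(1 − *r*)
- ANCOVA: *f* = 1 − *r*²

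By normal approximation the follow-up t-test detects 2.8016 × √(2/23) = 0.826 SD with 80% power; by noncentral t (44 df) it is 0.845. The change-score figure is 0.845 × √(2(1 − *r*)). The ANCOVA figure by noncentral t (43 df) is 0.806 / 0.732 / 0.604, multiplied by √(1 + 1/42) for chance baseline imbalance.

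| Assumed *r* | Follow-up t-test | Change t-test | ANCOVA | Gain over better t-test |
|---|---|---|---|---|
| 0.3 | 0.845 | 1.000 | 0.816 | 0.845 − 0.816 = 0.029 |
| 0.5 | 0.845 | 0.845 | 0.741 | 0.845 − 0.741 = 0.104 |
| 0.7 | 0.845 | 0.654 | 0.611 | 0.654 − 0.611 = 0.043 |

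**2. Open choice of test.** Simulated null trials with 23 per arm, five normal measurements and equal SDs give these chances of at least one p < 0.05 for one score:
- best of eight t-tests (four follow-up, four change): 0.276 / 0.272 / 0.257 under equal correlation of 0.3 / 0.5 / 0.7, and 0.266 / 0.257 / 0.242 under AR(1) with the same lag-one values
- month 6 fixed, score form open: 0.08 to 0.09
- one test fixed in advance: 0.05

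**3. The 0.20 screen.** From the seven listed items, 7 × 0.20 = 1.4 are expected to be selected by chance. A strongly prognostic item is left out about 1 − 0.20 = 80% of the time. Null trials were simulated with 23 per arm, a continuous outcome and seven independent candidates, two of them prognostic. The screen was compared with always adjusting for those two:

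| Assumed R-squared | Type I error, screen | SD of estimate, screen | SD of estimate, fixed list |
|---|---|---|---|
| 0.25 | about 0.04 | 0.29 | 0.26 |
| 0.50 | about 0.03 | 0.26 | 0.21 |

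The fixed-list SDs agree with √((2/23)(1 − R²)(1 + 2/41)) = 0.26 and 0.21. The screened estimate was centred on zero, so it is unbiased. Its test is conservative because a prognostic covariate tends to enter only when it is imbalanced, and the standard error is then too large on average. These figures are for a linear model at one visit; the logit mixed model for breast-feeding was not simulated.

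**The case against.** The strongest reply is that little depends on this. The scores are process variables in a pilot, the plan calls their analysis exploratory and post hoc, a t-test fixed in advance is valid, and the primary outcome has its own visit and test. All of that stands and it sets the severity. It does not remove the case for a better analysis of data already being collected.

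Four stronger readings are tempting, and the documents do not support them.

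- *The false-positive risk is about one in four.* The 0.24 to 0.28 assumes that all eight tests are run and only the best is reported, and nothing in the plan suggests this. Nor is it a ceiling, since the Exploratory Data Analysis section also leaves transformations open. It is an illustration.
- *The 0.20 screen biases the result or inflates error.* It does neither. The estimate is unbiased and the test errs on the conservative side. The loss is efficiency.
- *ANCOVA brings a large gain.* Comparing 0.61 with 0.84 SD at *r* = 0.7 ignores the change-score t-test, which the text equally allows and which already reaches 0.65.
- *The plan omits how follow-up scores are collected.* It says "The postpartum day 3 data collection will be done over the telephone" and places week 6 and months 3 and 6 at hospital visits. Only computer versus paper at those visits is unstated in the text, and Figure 5, which is not shown, may cover it.

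The support for particular covariates is also limited. The Background links maternal age to initiation and duration of breast-feeding, not to these scores. The Conceptual framework says that the self-efficacy scale reflects past experiences, which is not evidence that breast-feeding history predicts a follow-up score. Both are suggestions.

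**Conclusion.** The point holds as a minor one. The plan leaves the visit, score form and baseline term open for every continuous process score and selects exploratory covariates by chance imbalance. Both have a better alternative that needs no new variables.

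Against the better of the two permitted t-tests, ANCOVA lowers the detectable difference by about 0.03, 0.10 and 0.04 SD at *r* = 0.3, 0.5 and 0.7. The gain is small at either end and largest near *r* = 0.5. The screen costs precision and leaves type I error at about 0.03 to 0.04 rather than 0.05 when R-squared is 0.25 to 0.5.

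These sizes rest on assumed correlations and R-squared values, 23 women per arm, and the random assignment described in IV. Research Design and Methods. That section also calls the design quasi-experimental; if allocation were not random, imbalances would not be due to chance alone and the reasoning about the screen would need to be redone.

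**What to change.** Before any data are seen:

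1. Name one visit, chosen by the sponsor, for knowledge, self-efficacy and the continuous attitude and norm scores. Analyse each by ANCOVA of the follow-up score on group and baseline score, or by the mixed model with baseline score, time and group-by-time terms. Keep chi-square for the categorical parts.
2. Replace the 0.20 screen with a short pre-specified list of variables already collected, used whether or not the arms differ. Maternal age and previous breast-feeding history are candidates for the sponsor to confirm.
3. The plan gathers baseline after randomisation, on computer in one arm and on paper in the other. Unless baseline is completed before allocation or in the same mode in both arms, report the unadjusted follow-up comparison beside the ANCOVA without ranking the two, since a mode difference could enter through the baseline score.

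The cost is plan wording, one degree of freedom for the baseline score and two more if both suggested covariates are used, and the loss from ANCOVA of women with no baseline score.
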